5.2.3 Other Procedures

Tumor Biopsies

Participants with tumor accessible for an in-office biopsy (e.g a skin or vaginal lesion) will be offered the option of undergoing paired tumor biopsies. The initial biopsy will be performed after the patient has signed consent and has been registered for the study prior to administration of any drug. The second biopsy will be planned for week 2 following initiation of treatment, although this may be delayed until week 3 or week 4 if necessary due to scheduling considerations.

Participants who derive clinical benefit from the drug will be offered a biopsy at the time of progression, should they have disease that is safely accessible. Participants will be consented for this procedure. This biopsy should be performed within 6 weeks after progression.

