8.7 Specimen Requirements

Participation in the laboratory correlative study component of this study is mandatory for all participants. Additional details regarding correlative studies are outlined in Appendix H and the lab manual. The participating institution will collect and submit the patient's specimens as outlined below:

Required Specimen	Collection Time Point	Specific Instructions		
Archival Formalin-Fixed Paraffin-Embedded (FFPE) Tumor Required for Study Eligibility	Collected prior to initiating study treatment	1 st choice: block 2 nd choice: 25 unstained sections (10- 5 μm and 15- 10 μm)		
Pre-treatment Whole Blood	Collected prior to initiating study treatment	Blood drawn into two (2) EDTA tubes, 7-10 mL blood into each tube		

Required Specimen	Collection Time Point	Specific Instructions
Pre-treatment Plasma	Collected prior to initiating study treatment	7-10 mL drawn into appropriate plasma separator tube
Snap Frozen Primary Tumor ¹	Collected prior to initiating study treatment	N/A
Pre-treatment Biopsy ²	Collected after screening and prior to initiating study treatment	Minimum 3 cores: 1 FFPE 2 snap frozen
Post-treatment Biopsy ³	Collected at Cycle 1 between Days 8-15 ⁴ , after initiation of study treatment	Minimum 3 cores: 1 FFPE 2 snap frozen
Post-progression Biopsy ⁵	Collected within 6 weeks of progression	Minimum 3 cores: 1 FFPE 2 snap frozen

¹ If available from the participating institution's tissue banks

² Optional in participants with accessible, biopsiable lesions

- ³ Only in participants who had an initial pre-treatment biopsy. Post-treatment biopsy will not be required in participants who have had a complete response or whose tumor has responded such that lesions are no longer biopsiable.
- ⁴ Can be collected at any point during Cycle 1 between Days 8-15, preferred. If unable to collect during Days 8-15 for scheduling reasons, it will be acceptable to perform the biopsy between Days 15-28 of Cycle 1.
- ⁵ Optional in participants with accessible, biopsiable lesions

Shipping instructions for frozen samples will be clarified at a later time point.

Sites should send ambient FFPE biopsy samples directly to the Clinical Research Coordinator at the following address:

[name] Dana-Farber Cancer Institute [name] [contact] Email: [contact]

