10.1.2 Disease Parameters

Measurable Disease

Measurable disease is the presence of at least one (1) lesion that can be accurately measured in at least one dimension with longest diameter > 20 millimeters (mm) using conventional techniques (CT, MRI, x-ray) or ≥ 10 mm with spiral CT scan. Measurable lesions must be at least 2 times the slice thickness in mm. All tumor measurements must be recorded in millimeters (or decimal fractions of centimeters).

Lesions situated in a previously irradiated area will be considered measurable if there is objective evidence of progression of the lesion prior to study enrollment. Lesions in previously irradiated areas must be clearly identified as such.

Malignant lymph Nodes

To be considered pathologically enlarged and measurable, a lymph node must be ≥ 15 mm in short axis when assessed by CT scan (CT scan slice thickness recommended to be

no greater than 5 mm). At baseline and in follow-up, only the short axis will be measured and followed.

Non-measurable Disease

All other lesions (or sites of disease), including small lesions (longest diameter <10 mm or pathological lymph nodes with \geq 10 to < 15mm short axis, are considered non-measurable disease. Bone lesions, leptomeningeal disease, ascites, pleural/pericardial effusions, lymphangitis cutis/pulmonis, inflammatory breast disease, abdominal masses identified by physical exam that are not measurable by reproducible imaging techniques, and cystic lesions are all considered non-measurable.

Target Lesions

All measurable lesions up to a maximum of 2 lesions per organ and 5 lesions in total, representative of all involved organs, should be identified as target lesions and recorded and measured at baseline. Lesions must be accurately measured in 1 dimension with a minimum size of 10 mm by CT or MRI (slice thickness no greater than 5 mm), 20 mm by *chest* x-ray. Nodes must have a short axis ≥ 15 mm. The short axis should be included in the sum of the lesions in the calculation of response. Nodes that shrink to < 10 mm are considered normal. Target lesions should be selected on the basis of their size, be representative of all the involved organs, and should be lesions that can be followed with reproducible repeated measurements.

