10.3 Response Criteria

10.3.1 Evaluation of Target Lesions

Complete Response (CR):

Disappearance of all target lesions. Any pathological lymph node must have reduction in short axis to < 10 mm.

Partial Response (PR):

At least a 30% decrease in the sum of the diameters of target lesions, taking as reference the baseline sum diameters.

Progressive Disease (PD):

At least a 20% increase in the sum of the diameters of target lesions, taking as reference the smallest sum on study with at least a 5 mm absolute increase in the sum of all lesions. The appearance of one or more new lesions* denotes disease progression.

Stable Disease (SD):

Neither sufficient shrinkage to qualify for PR nor sufficient increase to qualify for PD, taking as reference the smallest sum diameters while on study.

Unknown (UN):

Assessment of target lesions cannot be made due to insufficient or unevaluable data. In this case, a concise explanation must be given.

Note: If tumor response data is missing for target lesions, the overall assessment must be UN unless there is new disease that would result in an overall assessment of PD. However, if there is missing or unevaluable data for non-target lesions, but data is available for all target lesions, the overall response for that time point will be assigned based on the sum LD of all target lesions. Additionally, the assessment of CR cannot be made if there is missing or unevaluable data for non-target lesions. In this case, the overall assessment would be PR.

*Definition of New Lesion: The finding of a new lesion should be unequivocal (i.e. not due to difference in scanning technique, imaging modality or findings thought to represent something other than tumor (ex: new bone lesions may be healing or flare of pre-existing lesions). However, a lesion identified on a follow-up scan in an anatomical location that was not scanned at baseline is considered new and will indicate PD. If a new lesion is equivocal (because of small size, etc.), follow-up evaluation will clarify if it truly represents new disease and if PD is confirmed, progression should be declared using the date of the initial scan on which the lesion was discovered.

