14.2 Statistical Analysis

The primary objective of this study is estimation of the best objective response rate (CR + PR) per RECIST 1.1. With the planned accrual of 35 participants to this single-arm trial, there is 91% power to detect an improvement in response rate from 0.07 to 0.22 using a one-sided 0.09-level exact binomial test. Therefore, the null hypothesis will be rejected if 5 or more participants respond to combination therapy with GSK1120212 and GSK2141795. The null hypothesis of 0.07 is based on a weighted average of the observed response rates from the 11 cohorts enrolled to GOG 127 and 227 series.

Secondary objectives include progression-free and overall survival, both of which will be estimated by the Kaplan-Meier method. PFS is defined as the time from registration to the study until documented disease progression or death without progression, whichever occurs first. Participants not experiencing a PFS event will be censored at the last date of documented disease evaluation. Overall survival is defined as the time from study registration to the time of death from any cause, with follow-up censored at the last date

known to be alive. Cox's proportional hazards models will be fitted to explore significant predictors of event-time endpoints.

Toxicity data will be tabulated and compared between any groups of interest using Fisher's exact tests, and will be routinely monitored, analyzed and reviewed by the DF/HCC DSMC.

Molecular correlative analyses will be conducted and all patient outcomes: response, PFS, OS and toxicity will be compared between the PIK3CA and RAS-isoform mutated and WT groups using the statistical methodologies specified above; estimating the proportion of participants harboring mutations in both genes is also of interest, as is comparing their outcomes to those in the remainder of the cohort. These analyses are considered exploratory and will not be adjusted for multiple comparisons.

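### No rule keeps a lesion biopsied between the baseline and first response scans out of the target sum, or tells the imaging core about it, so a procedure-induced change in diameter can enter the primary endpoint.

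*Combined protocol and SAP*

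**What the plan says.** **Target selection.** Section 10.1.2 (Target Lesions) takes "All measurable lesions up to a maximum of 2 lesions per organ and 5 lesions in total". On size it says: "Lesions must be accurately measured in 1 dimension with a minimum size of 10 mm by CT or MRI". An accessible measurable lesion is therefore a target by default unless the cap is reached.

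**Biopsies.** They are optional and offered where tumor can be reached in the office; Section 5.2.3 gives skin and vaginal lesions as examples, and Section 8.3 vaginal or cervical recurrence. On timing, Section 5.2.3 says: "The initial biopsy will be performed after the patient has signed consent and has been registered for the study". Section 8.7 places the pre-treatment sample after screening and the second sample in Cycle 1, preferably Days 8-15 and otherwise up to Day 28. The requirement each time is "Minimum 3 cores: 1 FFPE 2 snap frozen".

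**Response.** Under Section 10.3.1 a partial response is "At least a 30% decrease in the sum of the diameters of target lesions", relative to baseline. The Section 9 calendar sets response imaging at Days 22-28 of every even cycle. Sections 10.1 and 10.3.3 require confirmation at least four weeks later. Section 10.3.6 and Appendix H require central confirmation of every response; the listed submission is scans and radiology reports.

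**Decision rule.** Section 14.2: "the null hypothesis will be rejected if 5 or more participants respond to combination therapy".

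**The concern.** The primary endpoint is built from lesion diameters, and the trial's own procedure acts on some of those lesions between the two measurements being compared. With no control arm, a shift caused by the procedure cannot be separated from a drug effect. Tissue removal could lower the diameter. Swelling or bleeding could raise it, which might hide a true response or count towards progression.

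The success threshold is five responders, so a single misclassified participant has a visible effect on the chance of rejecting. Section 10.1.2 already restricts lesions in irradiated or loco-regionally treated areas, so the plan accepts that local intervention can make a lesion unsuitable. It does not extend that reasoning to its own biopsies.

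**Working it through.** **Step 1: the order of events.**
- Measurable disease is an entry criterion (Section 3.1.2) and all criteria must be met at registration (Section 4.2). Lesions are therefore measured before registration. Scans may be up to 28 days before therapy (Section 9).
- First biopsy: after registration and screening, before drug (Sections 5.2.3 and 8.7).
- Second biopsy: Cycle 1, Days 8-28 (Section 8.7).
- First response scan: Cycle 2, Days 22-28 (Section 9).

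Both biopsies lie between the baseline measurement and the first response measurement.

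**Step 2: the plan's own figure.** Section 14.2 states: "there is 91% power to detect an improvement in response rate from 0.07 to 0.22 using a one-sided 0.09-level exact binomial test". With n = 35 and rejection at 5 or more, the exact binomial tails are:
- P(X ≥ 5 | 35, 0.22) = 0.910, matching the stated 91%.
- P(X ≥ 5 | 35, 0.07) = 0.0948, which agrees with 0.09 only after rounding to two decimals.

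**Step 3: the diameter change needed for a spurious partial response.** For a biopsied lesion of d mm and other targets summing to m mm, the required fall is 0.30 × (d + m).

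| d (mm) | m (mm) | Fall needed (mm) | Can the biopsied lesion supply it alone? |
|---|---|---|---|
| 10 | 0 | 3.0 | yes |
| 15 | 0 | 4.5 | yes |
| 20 | 0 | 6.0 | yes |
| 10 | 20 | 9.0 | only by losing 90% of its diameter |
| 10 | 40 | 15.0 | no |

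The last column is arithmetic, not likelihood. The route is realistic mainly when the biopsied lesion is small and is the only target or most of the sum.

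**Step 4: one spurious response, taken as given.** One participant is already counted, so four true responders among the other 34 suffice: P(X ≥ 4 | 34, 0.07) = 0.212, against 0.095.

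**Step 5: not conditioning on the event.** Let b be the share of participants biopsied in a target lesion and s the chance that a biopsied non-responder is scored as a partial response. Neither is in the documents; both are assumed. The scored response rate under the null is 0.07 + 0.93 × b × s, and the type I error is P(X ≥ 5) among 35 at that rate.

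| b | s | Scored rate | Type I error |
|---|---|---|---|
| 0.10 | 0.01 | 0.0709 | 0.099 |
| 0.10 | 0.02 | 0.0719 | 0.103 |
| 0.20 | 0.02 | 0.0737 | 0.112 |
| 0.10 | 0.05 | 0.0747 | 0.117 |
| 0.10 | 0.10 | 0.0793 | 0.141 |
| 0.20 | 0.10 | 0.0886 | 0.194 |

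This calculation covers only falls in diameter. Any offsetting enlargement would reduce the inflation, and the documents give no basis for quantifying it.

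**The case against.** **Frequency and mechanism.** The biopsies are optional, uptake is not stated, and no core gauge or length is given. Nothing shows that cores shorten a longest diameter by 30%. If s is only 1-2%, the type I error barely moves: 0.099 to 0.112 across b of 10-20%. This stands, and it limits the size of the point.

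**Existing safeguards.** Section 10.1.2 asks for targets chosen by size that can be measured reproducibly, which lets an investigator pass over a small lesion due for coring. Responses are also confirmed and centrally reviewed. These safeguards help only in part. The selection text does not mention biopsy. A repeat scan guards against measurement noise, but removed tissue can still be absent at the repeat. The core receives no biopsy record under Appendix H.

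**Stronger readings that a reader might infer.** The documents do not support the following:
- That the biopsied lesions are small. No size is stated; 10 mm is only the floor for measurability, and a cervical or vaginal recurrence may be larger.
- That six cores come off one lesion. Section 5.2.3 speaks of paired biopsies, and Section 8.7 ties the second to a participant who had the first. Neither requires the same lesion.
- That the bias always favours the drug. Enlargement after biopsy is also possible.
- That one spurious response gives P(X ≥ 4 | 35, 0.07) = 0.227. That counts the spurious responder's place twice; the figure is 0.212.

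**Conclusion.** The gap is real. The plan lets a lesion biopsied between the baseline and first response scans stay in the target sum, and does not tell the imaging core which lesion it was. The primary endpoint can therefore absorb a change caused by the procedure, in either direction.

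The size is uncertain. The 0.212 is conditional on a spurious response having occurred, so it should not be read as the trial's error rate. Under the assumed inputs (b of 10-20%, s of 1-10%) the type I error is about 0.099 to 0.194, against 0.095 without the effect. The lower end is negligible, and the upper end rests on inputs that the documents neither support nor exclude. A reader might conclude that the trial's false-positive rate is more than doubled; the documents do not establish that.

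The point merits a change because the correction is cheap and alters no design figure, not because serious bias has been shown.

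**What to change.** Add to Section 10.1.2 (Target Lesions):
- A lesion biopsied, or planned for biopsy, after the baseline scan is recorded as non-target whenever another measurable lesion exists.
- If it is the only measurable lesion, it stays a target and is flagged on the case report form and in the Appendix H submission.

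Add to Section 14.2 a sensitivity analysis of the response rate in which a partial or complete response resting on a biopsied target lesion is not counted.

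Moving the first biopsy ahead of the baseline scan is not a substitute. It conflicts with the after-registration timing in Section 5.2.3 and leaves the Cycle 1 biopsy of a sole target untouched.

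**Cost.** A short text change, one form field, one line in the core submission and one extra analysis. A few participants lose a target lesion, and an organ may then be represented only by a non-target lesion, which cuts against the aim in Section 10.1.2 that targets represent all involved organs. The sample size of 35, the threshold of 5, the exact type I error of 0.0948 and the power of 0.910 are unchanged.

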10.2 Methods for Evaluation of Measurable Disease

All measurements should be taken and recorded in metric notation, using a ruler, calipers, or digital measurement tool. All baseline evaluations should be performed as closely as possible to the beginning of treatment and never more than 4 weeks before the beginning of the treatment.

The same method of assessment and the same technique should be used to characterize each identified and reported lesion at baseline and during follow-up. Imaging-based

evaluation is preferred to evaluation by clinical examination when both methods have been used to assess the anti-tumor effect of a treatment.

Chest X-ray

Lesions on chest x-ray are acceptable as measurable lesions when they are clearly defined and surrounded by aerated lung; however, CT is preferable.

Conventional CT and MRI

These techniques should be performed with cuts of 10 mm or less in slice thickness contiguously. Spiral CT should be performed using a 5 mm contiguous reconstruction algorithm. This applies to tumors of the chest, abdomen, and pelvis. Head and neck tumors and those of extremities usually require specific protocols. MRI is also acceptable in certain situations (e.g. for body scans).

Use of MRI remains a complex issue. MRI has excellent contrast, spatial, and temporal resolution; however, there are many image acquisition variables involved in MRI, which greatly impact image quality, lesion conspicuity, and measurement. Furthermore, the availability of MRI is variable globally. As with CT, if an MRI is performed, the technical specifications of the scanning sequences used should be optimized for the evaluation of the type and site of disease. Furthermore, as with CT, the modality used at follow-up should be the same as was used at baseline and the lesions should be measured/assessed on the same pulse sequence. It is beyond the scope of the RECIST version 1.1 guidelines to prescribe specific MRI pulse sequence parameters for all scanners, body parts, and diseases. Ideally, the same type of scanner should be used and the image acquisition protocol should be followed as closely as possible to prior scans. Body scans should be performed with breath-hold scanning techniques, if possible.

10.3 Response Criteria

10.3.1 Evaluation of Target Lesions

Complete Response (CR):

Disappearance of all target lesions. Any pathological lymph node must have reduction in short axis to < 10 mm.

Partial Response (PR):

At least a 30% decrease in the sum of the diameters of target lesions, taking as reference the baseline sum diameters.

Progressive Disease (PD):

At least a 20% increase in the sum of the diameters of target lesions, taking as reference the smallest sum on study with at least a 5 mm absolute increase in the sum of all lesions. The appearance of one or more new lesions* denotes disease progression.

Stable Disease (SD):

Neither sufficient shrinkage to qualify for PR nor sufficient increase to qualify for PD, taking as reference the smallest sum diameters while on study.

Unknown (UN):

Assessment of target lesions cannot be made due to insufficient or unevaluable data. In this case, a concise explanation must be given.

Note: If tumor response data is missing for target lesions, the overall assessment must be UN unless there is new disease that would result in an overall assessment of PD. However, if there is missing or unevaluable data for non-target lesions, but data is available for all target lesions, the overall response for that time point will be assigned based on the sum LD of all target lesions. Additionally, the assessment of CR cannot be made if there is missing or unevaluable data for non-target lesions. In this case, the overall assessment would be PR.

*Definition of New Lesion: The finding of a new lesion should be unequivocal (i.e. not due to difference in scanning technique, imaging modality or findings thought to represent something other than tumor (ex: new bone lesions may be healing or flare of pre-existing lesions). However, a lesion identified on a follow-up scan in an anatomical location that was not scanned at baseline is considered new and will indicate PD. If a new lesion is equivocal (because of small size, etc.), follow-up evaluation will clarify if it truly represents new disease and if PD is confirmed, progression should be declared using the date of the initial scan on which the lesion was discovered.

10.3.2 Evaluation of Non-Target Lesions

Complete Response (CR):

Disappearance of all non-target lesions and normalization of tumor marker level. All lymph nodes must be non-pathological in size (< 10 mm short axis).

Note: If tumor markers are initially above the upper normal limit, they must normalize for a subject to be considered in complete clinical response.

Incomplete Response/Stable Disease (SD):

Persistence of one or more non-target lesions and/or maintenance of tumor marker level above the normal limits.

Progressive Disease (PD):

Appearance of one or more new lesions* (new lesions must be > slice thickness) and/or unequivocal progression of existing non-target lesions.

Overall level of substantial worsening that merits discontinuation of therapy. A useful test that can be applied when assessing non-targets for unequivocal progression is to consider if the increase in overall disease burden based on the change in non-measurable disease is comparable in magnitude to the increase that would be required to declare PD for measurable disease.

Unknown (UN):

Assessment of non-target lesions cannot be made due to insufficient or unevaluable data. In this case, a concise explanation must be given.

*Definition of New Lesion: The finding of a new lesion should be unequivocal (i.e. not due to difference in scanning technique, imaging modality, or findings thought to represent something other than tumor (ex: new bone lesions may be healing or flare of pre-existing lesions). However, a lesion identified on a follow-up scan in an anatomical location that was not scanned at baseline is considered new and will indicate PD. If a new lesion is equivocal (because of small size, etc.), follow-up evaluation will clarify if it truly represents new disease and if PD is confirmed, progression should be declared using the date of the initial scan on which the lesion was discovered.

